 - Femoral offset should be determined by measuring the perpendicular distance from the center of the femoral head to the axis along the length of the femur.¹²
- Natural femoral neck angle (degrees)
 - Femoral neck angle is the angle between the long axes of the femoral neck and femoral shaft.¹³
- Qualitative assessment of natural femoral version (Retroverted, Neutral, Anteverted)
 - Proximal femoral version reflects the relationship of the axis of the femoral neck to the transcondylar axis of the distal femur.¹⁴ Qualitative determination of whether natural femoral version is retroverted, anteverted or in a state of neutral version should be made from the lateral radiograph.

The investigator at each center will create a preoperative biomechanical measurement plan for each case from templating, reflecting desired postoperative measurements and the component sizes, angles and offsets that will be used to achieve these measurements. All component sizes should be corrected for magnification (if any) prior to data collection on the study Case Report Form (CRF). This may be accomplished by utilizing an external radiographic marker of known dimension prior to taking the preoperative radiograph.¹⁵

CONFIDENTIAL

Preoperative Distance from Planned Center of Rotation

- Vertical distance from the anatomic hip center to the planned center of rotation of the hip (millimeters)
- Horizontal distance from the anatomic hip center to the planned center of rotation of the hip (millimeters)

Components to be Used

- Acetabular cup size
- Femoral neck angle [127°, 132°, 130° (16° version option only)]
- Femoral neck length (millimeters)
- Femoral head size
- Femoral head offset
- Femoral stem size*
- Femoral version (0°, ±8°, ±16°)

*The Rejuvenate® Modular Stem will be available in sizes 7, 8, 9, 10, 11 and 12. The Rejuvenate® Monolithic Stem will be available in sizes 4, 5 and 6; however, **the Rejuvenate® Monolithic Stem may not be used according to this protocol.** Patients requiring a femoral stem in size 4, 5 or 6 should not be enrolled into the study. Investigators should template the femoral stem size to be used prior to completing the Inclusion/Exclusion CRF for enrollment into the study.

Additional Planned Measurements

- Amount of leg length to be restored (centimeters)

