 - Measurement of leg length discrepancy should be determined from the AP pelvis radiograph by drawing lines across both pelvic teardrops to meet both femurs. These lines are to be used as the main reference lines for then measuring the distance to the top of each lesser trochanters.¹⁶ The difference between these distances is the value of leg length discrepancy. From this value, the investigator will determine the amount of leg length he/she plans to restore.
- Femoral offset to be achieved (millimeters)
- Qualitative assessment of postoperative planned femoral version (Retroverted, Neutral, Anteverted)

A postoperative check of biomechanical measurements will be performed by the investigator at each site from the 6-week radiographs to confirm the degree to which the

CONFIDENTIAL

preoperative plan was achieved. If an AE for instability exists, the postoperative check will be taken again at applicable postoperative intervals to confirm whether or not changes have occurred.

Postoperative Distance from Planned Center of Rotation

- Vertical distance from the postoperative hip center to the planned preoperative center of rotation of the hip (millimeters)
- Horizontal distance from the postoperative hip center to the planned preoperative center of rotation of the hip (millimeters)

Additional Postoperative Measurements

- Leg length discrepancy (centimeters)
- Final femoral offset (millimeters)
- Final femoral neck angle used [127°, 132°, 130° (16° version option only)]
- Qualitative assessment of replaced femoral version (Retroverted, Neutral, Anteverted)

These postoperative values will be compared to the preoperative plan to evaluate the degree of patient matching achieved with the Rejuvenate® Modular Hip System.

Component sizes used intraoperatively will be automatically determined from catalog numbers provided on the Surgical Details CRF.

Biomechanical measurements are outlined in Appendix B.

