9.1.2 Secondary Efficacy Parameters

The secondary efficacy parameters include:

- Biomechanical measurement change from preoperative plan at 6-week visit
- HHS at each visit
- SF-12 scores at each visit
- LEAS at each visit

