9.1.5 Secondary Efficacy Analysis

A two-sided 0.05 alpha level will be used.

For comparison of biomechanical measurements between a preoperative plan and postoperative measurements within the Rejuvenate[®] Modular Hip System group, a t-test or Wilcoxon test will be used.

Independent group t-tests will compare HHS, SF-12 and LEAS at each time point between the Rejuvenate[®] Modular Hip System and Secur-Fit[™] HA monolithic femoral stem groups. In addition, a paired t-test will compare the results preoperatively with each postoperative evaluation within the Rejuvenate[®] Modular Hip System group.

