D D M M M Y Y Y YOPERATIVE SIDE: Right Left
(use one form per side)VISIT:
 6 Week Unscheduled-
 Reviewer Collected**I. ACTUAL POSTOPERATIVE MEASUREMENTS****A. LEG LENGTH DISCREPANCY:**

Yes*
 No

* If Yes, indicate longer side:

Operative
 Contralateral

B. FINAL FEMORAL OFFSET: mm**C. QUALITATIVE ASSESSMENT OF REPLACED FEMORAL VERSION:**

Use the Lateral Radiograph:

Replaced femoral version: (Check one)

Retroverted
 Neutral
 Anteverted

D. POSTOPERATIVE DISTANCE FROM PLANNED CENTER OF ROTATION:

Vertical distance from the postoperative hip center to the planned preoperative center of rotation of the hip:

 mm

Horizontal distance from the postoperative hip center to the planned preoperative center of rotation of the hip:

 mm**II. COMMENTS**

--

INVESTIGATOR / REVIEWER
NAME (PRINT):INVESTIGATOR / REVIEWER
SIGNATURE:DATE: / / / / /
D D M M M Y Y Y Y

Stamp Date Received:

INITIAL/DATE:
Receipt _____

Entry _____

Verification _____
Monitored _____

For Stryker Use Only

Keep this reminder sheet in the subject's study binder.
Please do not send to Stryker.

Stryker®

REJUVENATE® MODULAR HIP SYSTEM
X-RAY REMINDER SHEET

[name]

Instructions for Stryker Orthopaedics Clinical Study X-ray Labels

1. Based on the protocol's radiographic evaluation schedule, obtain copies of the subject's X-rays.
 - a. If the subject is bilateral and the view includes both sides, **two** copies of the films are needed.
 - b. For viewing purposes, the film should always be the mirror image (not inverted).
 - i. If the subject's operative side is (R), the joint should be on the (L) side of the film when being viewed.
 - c. **Markers** for (R) and (L) should be on the correct side.
 - i. If incorrect or missing, the film should be marked correctly.
2. **Complete a white X-ray label** to ensure accurate identification of each film.
(similar to CRF header information)
 - a. Subject ID
 - b. Subject Initials
 - c. Date of X-ray
 - d. Visit Interval
 - e. Operative Side
 - f. View
3. **For films**, affix the label to the bottom of the film:
 - a. Should not obscure the view
 - b. Should not obscure the implant
 - c. Should not cover the subject imprint details
 - d. Should be positioned horizontally according to the view
4. **For digital X-rays**, attach completed unpeeled labels to the CD case and write the Subject ID on the CD.

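### The 6-week hip-centre distance is already the miss from plan, yet the plan compares it with the planned shift; it should be analysed directly as an error with target 0

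*Combined protocol and SAP*

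**What the plan says.** Section 2.1.2 defines two hip-centre items on each axis. The preoperative plan records "Vertical distance from the anatomic hip center to the planned center of rotation of the hip (millimeters", with a matching horizontal item. The 6-week check records "Vertical distance from the postoperative hip center to the planned preoperative center of rotation of the hip (millimeters", again with a horizontal counterpart. Sections 7.1 and 7.3 and Appendix B repeat these definitions. On the Appendix F forms the first is item E under the preoperative plan and the second is item D, "POSTOPERATIVE DISTANCE FROM PLANNED CENTER OF ROTATION".

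After listing the 6-week items, hip-centre distances included, section 2.1.2 says: "These postoperative values will be compared to the preoperative plan to evaluate the degree of patient matching achieved". Section 7.3 says the same. Section 9.1.2 names the secondary parameter as "Biomechanical measurement change from preoperative plan at 6-week visit". Section 9.1.5 reads "For comparison of biomechanical measurements between a preoperative plan and postoperative measurements within the Rejuvenate" group, "a t-test or Wilcoxon test will be used", at a two-sided alpha of 0.05. It does not say whether the test is paired or one-sample and gives no rule by variable. Section 2.1.2 expects the 6-week measurements to be similar to the plan, so no difference is the favourable reading.

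**The concern.** For leg length or offset, the planned and achieved values are the same kind of quantity and can sensibly be compared. The two hip-centre distances cannot. They share a reference point, the planned centre, but one measures how far the plan moves the hip and the other measures how far the result fell from the plan. Setting one against the other asks whether the miss equals the intended shift, which is not the question in the objective.

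At stake are the vertical and horizontal hip-centre results within the secondary objective on patient matching. A plan carried out exactly could be reported as different from plan, and a plan not carried out could be reported as similar to it. The recorded direction of the miss also matters: the readable text of the draft forms shows millimetres only for these items, whereas leg length has a choice of which side is longer.

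**Working it through.** The documents give no sample size, effect size or power for this comparison, so there is no figure to reproduce.

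**Inputs**
- A = anatomic centre, P = planned centre, Q = achieved centre at 6 weeks, on one axis.
- Preoperative value: pre = |P − A|. Six-week value: post = |Q − P| (section 2.1.2).
- Two-sided alpha 0.05 (section 9.1.5).
- 240 cases (section 3.3). The simulation uses 240 × 0.80 = 192 hips. The 20% loss is borrowed from section 9.4.2, where it applies to the 5-year endpoint, so it is an assumption here.
- Planned shift and placement error are not given. Both are assumed and varied.

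**Step 1: exact cases.** Take A = 0 and P = 8 mm.

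| Outcome | Q | pre | post | post − pre | true miss |
|---|---|---|---|---|---|
| Plan achieved exactly | 8 | 8 | 0 | −8 | 0 |
| Half the shift achieved | 4 | 8 | 4 | −4 | 4 |
| Centre left at anatomic position | 0 | 8 | 8 | 0 | 8 |
| Overshoot by 8 mm | 16 | 8 | 8 | 0 | 8 |

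The best outcome gives the largest difference, and two 8 mm misses give none. This needs only a planned shift other than 0. It does not need pairing, since the group values are 8 against 0 in the first row and 8 against 8 in the third.

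**Step 2: does signing help?** Take both distances as centre minus plan. Exact execution gives pre = 0 − 8 = −8 and post = 8 − 8 = 0, still a difference of 8. The ignored plan gives −8 and −8, still a match. If the preoperative value is signed the other way (+8), the ignored plan no longer matches, but exact execution still differs by 8. Signing alone does not make the comparison meaningful.

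**Step 3: with placement error.** Executed means Q = P + error. Ignored means Q = A + error. The error has mean 0 and the same SD in both arms. The test is a paired t-test of post against pre, 192 hips. The last two columns give the share of runs declared different.

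| Signed planned shift, mean (SD), mm | Error SD, mm | Executed | Ignored |
|---|---|---|---|
| 3 (3) | 1 | 100% | about 23% |
| 3 (3) | 2 | 100% | 69% |
| 8 (4) | 1 | 100% | about 5% |
| 0 (3) | 3 | 5% | 100% |

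A repeat of these four settings with 4,000 runs agreed to within about 2 percentage points. With all 240 hips, shift 5 (3) and error SD 1 mm, the mean difference was −4.3 mm for executed plans (100% flagged) and +0.03 mm for ignored plans (about 8% flagged).

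**Step 4: one-sample alternatives.** Suppose the 6-week distance alone is tested against 0.
- Unsigned: for normal error with SD s, the distance has mean s√(2/π) = 0.798s and SD s√(1 − 2/π) = 0.603s. With 192 hips, t ≈ (0.798 / 0.603) × √192 = 1.32 × 13.9 ≈ 18, whatever s is. The test rejects even when execution is right on average.
- Signed: executed plans are flagged in about 3–7% of runs, close to the nominal 5%. Ignored plans are flagged in 100% when the mean shift is 2, 5 or 8 mm. When the mean shift is 0, ignored plans are flagged in only about 4–6%, because opposite misses cancel. A measure of the size of the miss is therefore needed as well.

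**The case against.** The best counter-argument is that section 9.1.5 does not order this subtraction. It names no variables and does not call the biomechanical test paired, although the same section expressly uses a paired t-test for the outcome scores. For the hip centre, the 6-week distance already is the change from plan that section 9.1.2 names, so a one-sample analysis of it would fit the wording. That reading is possible and would remove the inversion. But section 9.1.5 describes a comparison between plan and postoperative measurements and does not state a one-sample form. On unsigned distances that form rejects under any realistic error (step 4).

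A reader might infer that the test reverses the answer whatever the values. The documents do not support that. The inversion is clear when planned shifts are large relative to placement error. With shift 0 (3) and error SD 3 mm, the test points the right way (5% against 100%). If the planned centre is the anatomic centre, the shift is 0 and exact execution gives 0 against 0.

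A reader might also infer that direction is certainly not recorded. The forms are drafts read by a program. The leg-length item shows no numeric field there although a value is required, so fields may have been lost. Section 11.4 also refers to a separate completion guide. Absence of a direction field is likely, not proven.

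Finally, the scope is small: two items in one single-arm secondary objective. Even without direction, the recorded distance gives the size of the miss.

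**Conclusion.** The point holds as a defect of definition. The plan-side and 6-week hip-centre distances are different quantities, and the text compares postoperative values with the plan without exempting them. Taken literally, exact execution of a non-zero planned shift counts as a difference, and a centre left at the anatomic position counts as a match. That follows from the definitions alone. The rejection rates do not: they rest on assumed normal shifts and errors, 192 hips and a paired t-test, and they run from 100% against about 5% (executed against ignored) to 5% against 100%.

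It would be too strong to conclude that the hip-centre part of the objective cannot be answered. The 6-week distance is the right measurement; what is missing is a statement of how to analyse it. The change should be made, but the primary endpoint and the other biomechanical items are unaffected.

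**What to change.** In sections 7.3, 9.1.2 and 9.1.5, exclude the vertical and horizontal hip-centre distances from the plan-versus-postoperative test. State that each 6-week distance is itself the error from plan, with target 0. Report, for each axis, the mean signed error with its 95% CI for systematic shift and the median absolute error for accuracy.

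Add a direction choice (superior or inferior, medial or lateral) to the hip-centre items on the preoperative and 6-week draft forms, or confirm that the forms or the completion guide already provide one.

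The cost is one tick-box per item and one sentence in the analysis section. No new films or visits are needed. If direction is left out now, recovering it later would mean measuring the films again.

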2.2 Safety

All operative site events as well as all serious adverse events (SAEs), excluding elective procedures, will be collected and compared to the historical control group and to published data. It is expected that the AE rates reported for the Rejuvenate® Modular Hip System will be comparable to those reported in the literature for similar modular stems and for the historical control group. For incidence of femoral neck fracture, a complication related to modularity, it is expected that rates reported for the Rejuvenate® Modular Hip System will be comparable to those reported in the literature for similar modular stems. Details regarding AE definitions, recording and reporting are in Section 8 of this protocol, Adverse Events.

CONFIDENTIAL

3 Clinical Study Plan

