Statistical Methodology	
Primary:
 
The 90% confidence interval around the difference in success rate (Rejuvenate® Modular Hip System – Secur-Fit™ HA monolithic femoral stem) will be computed at 5 years postoperative. For the non-inferiority comparison, the lower bound of this 90% confidence interval will be compared with -5%.
 
Secondary:
 
• A t-test or Wilcoxon test will be used to compare the postoperative biomechanical measurements to a preoperative plan.• Independent group t-tests will also compare HHS, SF-12 and LEAS at applicable time points between the Rejuvenate® Modular Hip System and Secur-Fit™ HA monolithic femoral stem groups. In addition, a paired t-test will compare the results preoperatively with each postoperative evaluation within the Rejuvenate® Modular Hip System group.• The adverse event (AE) rates and 95% confidence intervals will be presented within the Rejuvenate® Modular Hip System group. A Fisher's exact test will be used to compare the AE rates between the Rejuvenate® Modular Hip System and the Secur-Fit™ HA groups, if appropriate.• Radiographic data will be summarized in table format.
--------------------------------	---

CONFIDENTIAL

Evaluation Schedule

Evaluation	Preop X-rays (-1 yr) CRFs (-4 mos)	Intraop	6 weeks (± 3 wks)	1 year (± 2 mos)	2 years (± 2 mos)	3 years (± 3 mos)	4 years (± 4 mos)	5 years (± 4 mos)	6 years (± 4 mos)	7 years (± 4 mos)	8 years (± 4 mos)	9 years (± 4 mos)	10 years (± 4 mos)
Inclusion/ Exclusion	X												
Demographics & Medical History	X												
Preoperative Functional Evaluation	X												
Preoperative Biomechanical Measurements	X												
Surgical Details		X											
Postoperative Functional Evaluation			X	X	X	X	X	X		Optional			Optional
Postoperative Biomechanical Measurements			X										
SF-12	X		X	X	X	X	X	X		Optional			Optional
LEAS	X		X	X	X	X	X	X		Optional			Optional
Radiographs: Anteroposterior (AP) pelvis, AP femur, lateral	X		X	X	X	X	X	X		Optional			Optional
Follow-up Questionnaire									X	X	X	X	X

Functional Evaluation: The Functional Evaluations include the HHS, a subjective outcomes tool completed by the investigator that measures function, pain and motion.

SF-12: The SF-12 is a 12 item patient questionnaire that evaluates general health and well being.

LEAS: The LEAS is a self-administered patient evaluation designed to reflect patient activity.

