9.2.2 Safety Analysis

All AEs will be listed, tabulated and summarized by event, number and percent of cases/subjects. AE rates and 95% confidence intervals will be presented. In addition, a

CONFIDENTIAL

Fisher's exact test will be used to compare the AE rates between the Rejuvenate® Modular Hip System and the Secur-Fit™ HA groups or cohorts, if appropriate.

For categorical variables, such as radiographic stability, the number and percent in each category will be presented.

9.3 *Missing Data*

No missing data will be imputed for the primary analysis and secondary analyses.

9.4 *Statistical Methodology*

9.4.1 *Data Summary*

The following is a detailed proposal of statistical analyses planned for data collected during the study.

Descriptive statistics will be computed for all preoperative conditions and demographic parameters. That is, for continuous data (e.g. HHS) the N, mean, median, standard deviation, minimum and maximum will be computed. For categorical data (e.g. gender) the frequency will be computed. If appropriate, the data will be presented by the Rejuvenate® Modular Hip System and the Secur-Fit™ HA groups.

Descriptive statistics and statistical comparisons for important demographic, efficacy and safety variables will be provided in tables.

A survival analysis for revision/removal of the modular femoral stem/neck construct will be performed.

9.4.2 *Sample Size Calculation*

Given an estimated revision rate for both groups at 2.5% and a non-inferiority margin of 5%, with a one-sided alpha of 0.05 and 80% power, a total of 147 cases per group are required to reject the null hypothesis that the revision rate for Rejuvenate® Modular Hip System cases is 5% greater than for Secur-Fit™ HA monolithic femoral stem cases. In order to control for a 20% drop-out rate, 183 cases per group are required.

CONFIDENTIAL

A total of 240 cases received the Secur-Fit™ HA femoral stem in the Trident® X3® Polyethylene Insert Study, a historical control. Therefore, although only 183 cases are needed for statistical power, 240 cases will be enrolled in the Rejuvenate® Modular Hip System Outcomes Study.

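### Section 2.2 expects AE rates comparable to the Secur-Fit HA control, but the only between-group AE method named is a conditional Fisher test, with no interval for the difference

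*Combined protocol and SAP*

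**What the plan says.** Section 2.2 (Safety) says that operative-site events and serious AEs will be compared with the historical control and with published data. The expectation is put this way: "It is expected that the AE rates reported for the Rejuvenate® Modular Hip System will be comparable to those reported in the literature". The same sentence extends the expectation to the historical control. It does not say what would count as comparable.

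Section 9.2.2 (Safety Analysis) lists and tabulates AEs and presents rates with 95% confidence intervals. It adds one between-group method, due to Fisher and conditional on being suitable: an "exact test will be used to compare the AE rates between the Rejuvenate® Modular Hip System and the Secur-Fit™ HA groups or cohorts". The synopsis (Statistical Methodology) repeats the Fisher test with the same condition and says that AE "rates and 95% confidence intervals will be presented within the Rejuvenate® Modular Hip System group". Section 9.2.2 does not itself confine the intervals to one group, but neither place plans an interval for a difference or ratio between groups.

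No significance level is stated for safety. The nearest statement, "A two-sided 0.05 alpha level will be used", stands in Section 9.1.5 and concerns secondary efficacy.

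**The concern.** Fisher's test asks whether the data contradict equal rates. The expectation in Section 2.2 is a different matter: that the new device's rates are not materially higher than the control's. A non-significant test does not establish that, least of all for uncommon events in groups sized for another endpoint. The quantity a reader needs is the size of excess that the data leave open, and no planned between-group AE output shows it.

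The plan uses the suitable approach elsewhere: stem/neck revision is judged by a confidence bound on the difference (Section 9.1.4). Section 1.1 gives the study's purpose as showing that neck modularity has not changed survivorship, and Section 2.2 names femoral neck fracture as a complication of modularity. The safety comparison with the monolithic predecessor will therefore be read closely. If only p-values are reported, a large excess in a complication would often pass without comment.

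**Working it through.** **The plan's own figure.** The plan gives no power for any AE. Its sample size (Section 9.4.2) concerns revision only: 2.5% in both groups, 5% margin, one-sided 0.05, 80% power, 147 per group. The simple normal formula, (1.645 + 0.842)² × 2 × 0.025 × 0.975 / 0.05², gives 121. Exact enumeration with a 90% Newcombe interval first reaches 80% at n = 147 (power 0.807), so 147 is reproduced. With 20% drop-out, 147/0.8 = 183.75, against the stated 183. The 240 hips per group follow from the size of the control cohort (Section 9.4.2), not from any safety target.

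**Inputs for the AE check.**
- Group sizes: 240 and 240 (Section 9.4.2).
- Control rates: the sponsor column of Table 4 (Section 12.3). These pool seven studies and 2,966 hips, so their use for the control cohort is an assumption.
- Published dislocation averages: 6.1% and 2.23% (Table 4).
- Two-sided 0.05: assumed for AEs.
- Effect: a true doubling. This is my choice, because the documents give no safety effect size.

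**Method.** Power = Σ Bin(x; 240, 2p) × Bin(y; 240, p) over all pairs (x, y) with a two-sided Fisher p of at most 0.05. Miss rate = 1 − power.

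| Event | Control → study rate | Power | Miss |
|---|---|---|---|
| Dislocation | 3.30% → 6.60% | 31.5% | 68.5% |
| Dislocation, lower published average | 2.23% → 4.46% | 19% | 81% |
| Dislocation, higher published average | 6.1% → 12.2% | 59% | 41% |
| Femoral crack/fracture (surgery-related) | 3.78% → 7.56% | 36.5% | 63.5% |
| Postoperative femoral fracture | 1.01% → 2.02% | 6.4% | 93.6% |

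Part of the loss comes from the conservatism of Fisher's test: at equal rates of 3.30% its actual two-sided error is 2.6%. An uncorrected normal approximation still gives only 38%, 43% and 15% power at the three sponsor rates. At 240 per group, Fisher's test reaches 80% power only at about a 3.0-fold rise in dislocation, 2.9-fold in femoral crack/fracture and 5.8-fold in postoperative femoral fracture. For a doubling of dislocation, 80% power needs about 678 hips per group by the normal approximation.

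**What an interval would add.** Suppose 16/240 against 8/240 dislocations (6.667% v 3.333%). Fisher gives p = 0.14. The Wilson 95% limits are 4.145% to 10.554% and 1.699% to 6.438%. The Newcombe limits for the difference are:
- upper: 3.333 + √[(10.554 − 6.667)² + (3.333 − 1.699)²] = 3.333 + 4.217 = +7.6 points (7.55 before rounding)
- lower: 3.333 − √[(6.667 − 4.145)² + (6.438 − 3.333)²] = 3.333 − 4.000 = −0.7 points

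The p-value alone would pass unremarked, while the interval shows that an excess of up to 7.6 points is not excluded. Even with 8 against 8 the interval is about ±3.5 points, wider than the 3.30% base rate.

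**The case against.** The strongest reply is that the plan contains no faulty decision rule. A reader might infer that a Fisher p-value above 0.05 will be reported as comparability, but no section says so. Section 2.2 states an expectation, and the test is conditional. Leaving AEs descriptive and unpowered in a study sized on revision is a legitimate choice. This stands, and the point is limited accordingly: the between-group measure is missing, but no rule is shown to be wrong.

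A reader might also infer that the plan can never show how large an excess remains possible. That goes too far. Sections 2.2 and 12.3 also set the device against published rates, and the Rejuvenate intervals serve that purpose. For example, 8/240 dislocations gives an exact 95% interval of 1.4% to 6.5%. With 16/240 it is 3.9% to 10.6%, whose lower limit lies above Table 4's 3.30%. Revision, a listed safety parameter, has a between-group interval against a margin, and Section 9.4.1 promises unnamed statistical comparisons of important safety variables. The gap is therefore confined to AE rates against the historical control.

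The base rates are also open to challenge, since the seven pooled studies collected AEs under different rules (note to Table 4). The range of 41% to 81% for dislocation shows how far the figure moves. Allowing for drop-out (192 per group) would raise the sponsor-rate miss rates to 76%, 72% and 96%. I do not rely on those figures, because safety is analysed in the modified ITT population of implanted cases (Section 9.4.4).

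Finally, it is tempting to borrow the 5-point primary margin as a test of comparability. It does not suit rare events. At Table 4 sponsor rates and 240 per group, requiring a 95% Newcombe upper limit below 5 points would declare comparability after a true tripling in 88% of trials for deep infection, 99% for femoral loosening and 50% for postoperative femoral fracture. The primary margin is also inconsistent within the plan: 7% in Section 9.1.3, but 5% in Sections 9.1.4 and 9.4.2 and the synopsis.

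**Conclusion.** The concern holds in this limited form. For AE rates against the Secur-Fit HA control, the plan names a test of difference and no estimate of the difference, although Section 2.2 expects comparability. At 240 per group that test misses a doubling of dislocation about 69% of the time (41% to 81% over the published averages), of surgery-related femoral crack/fracture 64%, and of postoperative femoral fracture 94%. These figures rest on pooled sponsor rates standing in for the control cohort, an assumed two-sided 0.05 and full group sizes. The primary analysis is unaffected. The documents do not support a claim that the plan equates non-significance with comparability, nor a fixed 5-point rule for AEs. This is an inexpensive improvement in reporting that makes the safety comparison interpretable.

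**What to change.** In Section 9.2.2 and the synopsis:

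1. For the main operative-site and device events in Table 4 (dislocation, surgery-related femoral crack/fracture, postoperative femoral fracture, deep joint infection, femoral component loosening), report the rate difference, Rejuvenate minus Secur-Fit HA, with a 95% Newcombe interval alongside any Fisher p-value.
2. State that a non-significant Fisher result is not evidence of comparability.
3. Word the safety conclusion by the upper limit, that is, by the largest excess over the control that the data do not exclude. Set no common comparability margin.

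The cost is a few sentences and a few intervals from data already collected, with no added patients or visits. The downside is that for some events the report must say that a sizeable excess was not ruled out.
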